14.1.2 SECONDARY EFFICACY ENDPOINTS AND ANALYSES

1. Proportion of patients with undetectable SARS-CoV-2 at PCR at day 14 after randomization at day 28 after randomization. Analyses will be performed on FAS population. This endpoint will be derived as below

- Based on Approved molecular test (PCR) result, the responses will be considered as “detectable” if PCR result is “Positive” otherwise “undetectable” if PCR result is “Negative” (Missing PCR result will be considered as missing).

The response (detectable / undetectable) at day 14 and day 28 will be analysed using repeated measures logistic regression model with treatment group, visit and pre-defined baseline factors (center, age and status). Odds ratio will be computed for comparisons of each active treatment group versus placebo at each assessment day i.e., raloxifene (60 mg) versus placebo; and raloxifene (120 mg) versus placebo. Analyses will be performed on FAS population using observed data only.

2. Proportion of patients who does not require supplemental oxygen therapy (NEWS ≤ 2) and mechanical ventilation at day 7 and 28 after randomization. This endpoint will be derived as below

- If collected NEWS score > 2 or mechanical ventilation with result “Yes” then the response will be considered as “Required”. If collected NEWS score ≤ 2 and mechanical ventilation with result “No” then the response will be considered as “Not Required” (if both NEWS score and mechanical ventilation are missing, patient will be considered as missing).

The response (Required / Not Required) at day 7 and day 28 will be analysed using repeated measures logistic regression model with treatment group, visit and pre-defined baseline factors (center, age, status and baseline NEWS). Odds ratio will be computed for comparisons of each active treatment group versus placebo at each assessment day. i.e., raloxifene (60 mg) versus placebo; and raloxifene (120 mg) versus placebo. Analyses will be performed on FAS population using observed data only.

For the above two secondary endpoints, Repeated Measures Logistic regression will be performed using PROC GENMOD in SAS® on the observed data only to estimate difference in proportions between each active treatment versus placebo and its corresponding 95% (2-sided) confidence intervals. Exponential transformation will be used to obtain the odds ratio and corresponding 95% confidence interval. P-values will be reported based on the Wald tests from Type III analyses.

In the SAS® procedure PROC GENMOD, a Type III analysis will be performed by adding the model options: TYPE3, DIST=BIN and LINK=LOGIT. REPEATED statement will be used to consider visit and TYPE=UN option used for correlation-matrix. If the model does not converge then appropriate TYPE would be applied for correlation-matrix.

The following time-to-event endpoints will be analysed according to SAP section 4.4 methods.

- i. Time to reach undetectable SARS-CoV-2 at PCR
- ii. Time to get relieved from supplemental oxygen therapy (NEWS ≤ 2) and/or mechanical ventilation
- iii. Overall survival

Analyses will be performed on FAS population.

3. Proportion of patients in each NEWS category at Day 7, 14 and 28 after randomization will be summarized by frequency and percent by treatment and visit for FAS population.
4. NEWS score at Day 7, 14 and 28 after randomization will also be summarized using descriptive statistics by treatment and visit for FAS population.
5. Proportion of hospitalized patients who at the beginning of the study were at domicile isolation at day 7, 14 and 28 after randomization will be analysed using comparison of proportions (i.e comparisons of each active treatment group versus placebo at each assessment day) through Fisher's exact test and will be summarized using frequency and percent by treatment and visit. Analyses will be performed on FAS population.

6. Proportion of patients admitted to intensive care at Day 7, 14 and 28 after randomization will be analysed using comparison of proportions (i.e comparisons of each active treatment group versus placebo at each assessment day) through Z-test and will be summarized using frequency and percent by treatment and visit. Analyses will be performed on FAS population.
7. Overall survival will be analysed according to time-to-event methods described in SAP section 4.4.
8. Quality of life questionnaire (EQ-5D-5L) at 3 months after the randomization will be summarized using appropriate descriptive statistics by treatment. The number and proportion of subjects of each level (1 - no problems, 2 - slight problems, 3 - moderate problems, 4 - severe problems, 5 - extreme problems) for each dimension (mobility, self-care, usual activities, pain/discomfort, and anxiety/depression) will be reported.
Analyses will be performed on FAS population.

Patient's data will be listed for all secondary endpoints.

Additionally, conformed SARS-COV-2 infection listing will be provided for ENR population. Confirmation of SARS-CoV-2 infection must be available before the screening visit i.e Pre-screening. Only diagnosed COVID-19 paucisymptomatic patients will be evaluated for the trial participation.

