9.5. STATISTICAL METHODOLOGY

All patient data collected on the eCRF will be listed by patient and center.

Appropriate descriptive statistics will be produced, according to the variable:

- for continuous data n, mean, standard deviation (SD), median and range (minimum and maximum) will be presented;
- for categorical data, frequency distributions and percentages will be presented;
- for time-to-event variables, cumulative freedom from event will be evaluated using Kaplan-Meier method. The degree of uncertainty will be expressed with 95% confidence limits (calculated per the method proposed by Greenwood). Comparison of curves among arms will be performed with the log-rank test. Kaplan-Meier graphs will be presented along with the number of patient-at-risk at exact time points. Subjects ongoing and who are free from event at the time of DB lock will be censored at the DB lock date. Subjects who have discontinued without an event will be censored at the date of discontinuation.

Unless otherwise specified, the significance level used for statistical testing will be 0.05 and two-sided tests will be used.

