9.5.2.2. Secondary analyses

All secondary endpoints will be analyzed at each available timepoints by means of descriptive statistics and by appropriate parametric tests depending on the nature of the variable and its distribution. Data transformation might be used in order to satisfy the assumption of normality requested by parametric statistical tests. In case such assumptions are not met, non-parametric counterpart tests will be used. Change from baseline value (for continuous variables) and shift tables versus baseline (for categorical variables) will also be summarized for all post-baseline visits.

The incidence of participants with undetectable SARS-CoV-2 at PCR, the incidence of participants who requires supplemental oxygen therapy (NEWS ≤ 2) and/or mechanical ventilation, and mortality will be analyzed as proportion at each time point and as time-to-event.

Details will be provided in the SAP.

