3.1.2 SECONDARY OBJECTIVES

- Evaluation of the effectiveness of therapy in reducing the proportion of patients who still have viruses in the upper airways after 14 and 28 days of therapy.
- Evaluation of the effectiveness of therapy in reducing the proportion of patients who requires supplemental oxygen therapy and/or mechanical ventilation within 7 or 28 days of starting therapy.
- 7, 14 and 28 days drug safety and tolerability profile.
- Assessment of body temperature, blood and biochemical parameters between T0 and T28.

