4.4 OVERALL ANALYSIS

Final analyses identified in this SAP will be performed by Agati Clinical Informatics following Sponsor Authorization of this Statistical Analysis Plan, Database Lock, Sponsor Authorization of Analysis Population and Unblinding of Study Treatment.

For primary and secondary efficacy endpoints, p-value, lower and upper 95% Confidence Limits (CL) will be also presented based on the statistical analysis performed.

The default summary statistics for quantitative variables will be the number of observations (n), mean, standard deviation (SD), median, minimum (min) and maximum (max).

For qualitative variables, the number (n) and percentage (%) of patients with non-missing data per variable of interest will be the default summary presentation, if appropriate and wherever required the number of missing values will be presented as a "Missing" category. If appropriate, 95% confidence intervals around the percentage will be presented.

Time-to-event endpoints will be assessed by the Kaplan-Meier (K-M) method. Time to event curves will be compared (i.e comparisons of each active treatment group versus placebo) using log-rank test and estimates of hazard ratio will be obtained using Cox proportional hazards model after performing diagnostics of proportional hazard assumption (investigated with a time dependent exploratory variable treatment*{log[time to event]}); if the p-value from the Wald Chi-squared statistic for this variable is less than 5% there is evidence of a departure from the adjusted model assumptions.). K-M estimates of median survival time associated with each treatment group will be provided along with 25th and 75th percentiles and their 2-sided 95% CIs (based on Greenwood's method). K-M estimates will be presented at Day 7, 14 and 28 for each treatment group. K-M curves will be plotted comparing treatment groups with the number of patient-at-risk in each treatment group at exact time points. Patients who are ongoing and who are free from event at the time of DB lock will be censored at the DB lock date. Patients who have discontinued without an event will be censored at the date of discontinuation. Patients who are died will be considered as censored with death

date as date of censored.

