14.1.1 PRIMARY EFFICACY ENDPOINTS AND ANALYSES

1. Proportion of patients with undetectable SARS-CoV-2 at PCR at day 7 after randomization (virologic endpoint). This endpoint will be derived as below.
 - Based on Approved molecular test (PCR) result at day 7, the responses will be considered as “detectable” if PCR result is “Positive” otherwise “undetectable” if PCR result is “Negative” (Missing PCR result will be considered as missing in the main analysis).

The response (detectable / undetectable) at day 7 will be analysed using Binary logistic regression model with treatment group and pre-defined baseline factors (center, age, status and their interaction effects with treatment group). Odds ratio

will be computed for comparisons of each active treatment group versus placebo. i.e., raloxifene (60 mg) versus placebo and raloxifene (120 mg) versus placebo.

2. The proportion of patients who does not require supplemental oxygen therapy (NEWS ≤ 2) and mechanical ventilation at day 14 after randomization (clinical endpoint). This endpoint will be derived as below.

- If collected NEWS score > 2 or mechanical ventilation at day 14 result “Yes” then the response will be considered as “Required”. If collected NEWS score ≤ 2 and mechanical ventilation with result “No” then the response will be considered as “Not Required” (if both NEWS score and mechanical ventilation are missing, patient will be considered as missing).

The response (Required/ Not required) at day 14 will be analysed using Binary logistic regression model with treatment group and pre-defined baseline factors (center, age, status, baseline NEWS and their interaction effects with treatment group). Odds ratio will be computed for comparisons of each active treatment group versus placebo. i.e., raloxifene (60 mg) versus placebo; and raloxifene (120 mg) versus placebo.

For both virologic and clinical endpoint, Binary Logistic regression will be performed using PROC GENMOD in SAS® on the observed data only to estimate difference in proportions between each active treatment versus placebo and its corresponding 95% (2-sided) confidence intervals. Exponential transformation will be used to obtain the odds ratio and corresponding 95% confidence interval. P-values will be reported based on the Wald tests from Type III analyses. Bonferroni method will be considered to handle multiple treatment comparisons.

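### The SAP replaces the protocol's time to needing oxygen or ventilation with time to being relieved of it, in patients who enter without that need, and does not list the change

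*SAP*

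**What the plan says.** Protocol 9.5.2.2 names three quantities to be analysed both as proportions and as time-to-event: undetectable virus, "the incidence of participants who requires supplemental oxygen therapy (NEWS ≤ 2) and/or mechanical ventilation", and mortality.

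SAP 14.1.2 lists three time-to-event endpoints: time to undetectable virus, "Time to get relieved from supplemental oxygen therapy (NEWS ≤ 2) and/or mechanical ventilation", and overall survival. SAP 14.1.3 times the second from treatment start to the date of relief or censoring, plus one day. The analysis set is the FAS.

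The SAP's own secondary objective (3.1.2) speaks of "reducing the proportion of patients who requires supplemental oxygen therapy and/or mechanical ventilation within 7 or 28 days of starting therapy". Its binary endpoints follow the same direction. The day-14 rule in 14.1.1 opens "If collected NEWS score > 2 or mechanical ventilation at day 14 result", the day-7 and day-28 rule in 14.1.2 opens "If collected NEWS score > 2 or mechanical ventilation with result", and a patient who meets either condition is classed as Required.

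Protocol 4.1 and 4.2 admit only patients with no need of oxygen or ventilation. Protocol section 4 defines a paucisymptomatic case as having NEWS ≤ 2.

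On censoring, SAP 4.4 says "Patients who are ongoing and who are free from event at the time of DB lock will be censored at the DB lock date", as Protocol 9.5 does ("Subjects ongoing and who are free from event at the time of DB lock will be censored at the DB lock date"). SAP 4.4 also says "Patients who are died will be considered as censored with death", the sentence going on to make the date of death the censoring date. SAP section 18 lists four changes from the protocol, and none concerns a time-to-event endpoint.

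**The concern.** The trial asks whether treatment keeps mildly ill patients from needing respiratory support. A time-to-event analysis of that question has onset of need as its event, and an effective drug delays or prevents it. The SAP makes leaving that state the event, in people who have not entered it. The Kaplan-Meier, log-rank and Cox output would then be degenerate, or would record as successes some patients who later deteriorate. Because section 18 is silent, a reader of the study report could take the result for the analysis the protocol planned.

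**Working it through.** The plan gives no event count, hazard ratio or power for this analysis, so there is no stated figure to reproduce. The check is mainly a comparison of the texts.

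**Which direction did the protocol intend?** The NEWS ≤ 2 tag in Protocol 9.5.2.2 sits beside the word for requiring support. Everywhere that the endpoint is defined (Protocol 7.1.1, SAP 3.2.1, SAP 14.1.1), NEWS ≤ 2 marks the state of *not* requiring it. The tag is a slip. The verb, the objectives and the protocol's description of Kaplan-Meier curves as freedom from event (9.5) all point to onset.

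**What does the SAP event mean in this population?** Three readings are possible, and the SAP does not choose among them.

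1. *The T0 status counts.* Essentially everyone has the event at time zero, and there is no contrast between arms.
2. *Only post-baseline records count (SAP 7.2.2).* Anyone not worse at T7 has the favourable event then, including patients who need oxygen later.
3. *Relief means coming off support.* Nobody is at risk at time zero. The risk set is a post-randomisation subset. Under Protocol 6.2.4 patients are withdrawn when need arises, and SAP 4.4 censors discontinuations, so on those two passages relief might never be observed.

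Onset is the event in none of the three.

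**Illustration of reading 2.** Inputs: 68 patients (SAP 4.3), assumed equally split and all assessed; day-14 need of 50% on placebo and 25% on active (complements of the 50% and 75% in SAP 4.1.2), treated as need present at day 14; and a share f of that need already present at T7. The documents do not give f.

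- Patients per arm: 68/3 = 22.67.
- In need at day 14: placebo 0.50 × 22.67 = 11.33; each active arm 0.25 × 22.67 = 5.67.
- Recorded as relieved at T7 but in need at day 14: p(1 − f) × 22.67, where p is the day-14 need.
- Their share of all T7 relief events, if T7 need persists to day 14: p(1 − f)/(1 − pf).

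| f | Placebo, of 11.33 | Each active arm, of 5.67 | Placebo share | Active share |
|---|---|---|---|---|
| 0 | 11.33 | 5.67 | 50% | 25% |
| 0.25 | 8.50 | 4.25 | 43% | 20% |
| 0.50 | 5.67 | 2.83 | 33% | 14% |
| 0.75 | 2.83 | 1.42 | 20% | 8% |
| 1 | 0 | 0 | 0% | 0% |

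Under constant hazards f differs by arm. The proportion with onset by day 7 is 1 − √0.50 = 0.293 on placebo and 1 − √0.75 = 0.134 on active, so f is 0.293/0.50 = 0.59 and 0.134/0.25 = 0.54. The later progressors are then (0.50 − 0.293) × 22.67 = 4.7 on placebo, a share of 0.207/0.707 = 29%. In each active arm they are (0.25 − 0.134) × 22.67 = 2.6, a share of 0.116/0.866 = 13%.

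**The corrected event, on the same assumptions.** The hazard ratio is ln 0.75 / ln 0.50 = 0.415, and 11.33 + 5.67 = 17 events are expected by day 14 per dose-placebo comparison. By Schoenfeld's formula, power is about 44% at two-sided 0.05. Even when correctly defined, this analysis can only be supportive.

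**The case against.** The best case for leaving this alone has four parts.

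*The protocol left details to the SAP, and its own wording is confused by the NEWS tag.* True, and the tag may be where the relief wording came from. But supplying details does not extend to reversing the event. Even if the tag is taken at face value, it describes staying free of need, not being relieved of support that nobody is receiving.

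*NEWS ≤ 2 is a definition, not a numbered inclusion criterion, and screening can precede T0 by up to seven days.* This stands as a limit. A few patients could have a T0 NEWS above 2 and be genuinely at risk of improving. It does not rescue the endpoint for the rest.

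*Little depends on it.* This also stands. No time-to-event measure appears in either document's endpoint list, and progression is examined in several other ways.

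*Counting need only at scheduled visits would itself mislead.* This is right, and it shapes the fix. A patient who meets the criteria on day 10 and is withdrawn under Protocol 6.2.4 may have no T14 record. Censoring at the last need-free visit would then treat that patient as event-free.

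A reader might also infer from SAP 4.4 that overall survival will be analysed with no events at all. Read literally, 4.4 says so, and 14.1.2 sends overall survival to 4.4. But the specific derivation in SAP 14.1.3 puts the date of death where the event date belongs, and Protocol 9.5.2.2 and 9.5.4 plan mortality and overall survival as time-to-event. It is a wording conflict with an obvious intended answer.

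**Conclusion.** The point holds. The SAP reverses a protocol-planned event, does so without listing it, and as written gives output that is degenerate or answers another question. It should be corrected before unblinding.

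Its reach is one supplementary secondary analysis. A reader might infer that the trial no longer examines progression. The documents do not support that: need for support at days 7, 14 and 28, hospitalisation and ICU admission are all still compared, and deaths are counted and listed (SAP 14.1.1, 14.1.2, 15.1.2). The primary analyses are untouched.

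The counts of later progressors recorded as relieved are not estimates. Across the possible values of f they run from none to all, and they apply only under the second reading. They rest on planning rates, equal arms and complete assessment. What they show is direction: at the planning rates and any common f below 1, such patients form a larger share of the favourable events on placebo than on active treatment, which could mask a benefit. No figure is claimed for overall survival.

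**What to change.** In SAP 14.1.2 and 14.1.3:

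- Define the event as first documented need for oxygen or ventilation, using the SAP's own Required rule (NEWS > 2, or mechanical ventilation recorded as Yes). The tags in Protocol 9.5.2.2 (NEWS ≤ 2) and in the Protocol section 2 schedule (NEWS ≥ 2) do not agree with that rule or with each other, so state the condition once.
- Count need recorded at T7, T14 or T28. Also count as an event, at the discontinuation date, any patient withdrawn because the need criteria were met, so that progressors between visits are not censored as event-free.
- Censor only patients with no documented need, at their last assessment of need. State that for this endpoint this replaces the database-lock and discontinuation rules of SAP 4.4 and Protocol 9.5.
- State how death before need is handled, since treating it as ordinary censoring would be informative.

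Enter the change in section 18 before unblinding. Protocol 6.2.4 (withdrawal from the study when need arises), Protocol 6.3 (patients who stop study drug stay in follow-up) and SAP 7.3.2 (disease progression listed as a reason for stopping treatment but not for leaving the study) differ on what follows once need arises, and must be reconciled.

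As a minor wording correction, add to SAP 4.4 that the death-censoring sentence does not apply to overall survival, where death is the event, as 14.1.3 already implies.

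The cost is SAP text, derivation code and the section 18 entry. Scheduled-visit records and discontinuation dates and reasons are already part of the plan. The reason must identify withdrawals for need. A more exact onset date can be used only if the eCRF collects one, which the documents do not show.

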All secondary endpoints will be analysed at each available timepoint by means of descriptive statistics and by appropriate parametric tests. Change from baseline value and shift tables versus baseline will be summarized for all post-baseline visits, if applicable.

AEs will be presented in terms of the number of AEs and incidence. Other safety parameters will be summarized by treatment at each available visit by means of descriptive statistics.

The Safety and the Full Analysis Set population will consist of all patients who will be randomized and received at least one dose of the investigational product. Safety population will be analysed according to the actual treatment received; Full Analysis Set population will be analysed according to ITT principle, i.e. by treatment allocation. Primary and secondary efficacy analyses will be conducted on the FAS population while the SAF population will be used for safety analyses.

A Statistical Analysis Plan (SAP) will be issued with more technical and detailed elaboration of the principal features of statistical analyses. Any deviation from the original statistical plan will be described in the Clinical Study Report.

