15.2 VITAL SIGNS

The following vital signs (blood pressure [BP], pulse rate [PR], body temperature [BT]), transdermal oxygen saturation (SpO₂) will be collected for patients.

Vital signs measurements will be summarized by treatment using descriptive statistics for each available visit, including change from baseline.

All vital signs findings will be listed, including data from the unscheduled visits.

15.3 LABORATORY PARAMETERS: BLOOD (HEMATOLOGY & BIOCHEMISTRY), COAGULATION, VIROLOGY AND OTHER MARKER

The following biomarker parameters at Day 7, 14, 21 and 28 after randomization will be summarized using descriptive statistics by visit and treatment:

- Complete blood cell counts
- Hepatic function (ALT, AST and bilirubin)
- Coagulation (PT, aPTT and INR)
- Other marker including (D-dimer, CPK, LDH)

Depending on the nature of the variable (continuous or categorical) the change from baseline values or shift tables comparing baseline and each post-baseline qualitative results of laboratory findings will be presented.

Mean (+/-) Standard Error Plot will be plotted for the change from baseline results of the above-mentioned laboratory parameters by visit and treatment. Analyses will be performed on SAF population.

Actual results and change from baseline for quantitative laboratory parameters will be summarised descriptively by treatment and visits. In addition, shift tables for laboratory parameters comparing values (Low, Normal and High) using the standard reference ranges will be presented for the baseline laboratory measurements vs. each post-baseline visit measurements.

Additionally, the frequency of patients reporting an abnormal or abnormal clinically significant laboratory value will be presented for each laboratory parameter.

For any Patient, if more than 1 results per visit and per lab parameters are available then the latest one will be considered based the date and time.

All laboratory results will be listed.

The below list of lab parameters results will be collected for patients.

Table 4: List of Lab parameters

Biochemistry (T0, T7, T14, T21, T28)	Haematology (T0, T7, T14, T21, T28)	Coagulation (T0, T7, T14, T21, T28)

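### The SAP drops the protocol's tests for NEWS score, NEWS category and EQ-5D-5L without declaring it, so NEWS is compared between arms only after being cut at 2

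*SAP*

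**What the plan says.** Protocol section 9.5.2.2 states: "All secondary endpoints will be analyzed at each available timepoints by means of descriptive statistics and by appropriate parametric tests". It adds a fallback: "In case such assumptions are not met, non-parametric counterpart tests will be used". The synopsis repeats the commitment: "All secondary endpoints will be analysed at each available timepoint by means of descriptive statistics and by appropriate parametric tests". The secondary endpoints in Protocol section 7.1.2, carried over into SAP section 3.2.2, include NEWS category, mean NEWS, biomarker change and quality of life.

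SAP section 14.1.2 treats these endpoints as follows:

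- Item 3: NEWS category "will be summarized by frequency and percent by treatment and visit for FAS population".
- Item 4: "NEWS score at Day 7, 14 and 28 after randomization will also be summarized using descriptive statistics by treatment and visit for FAS population".
- Item 8: "Quality of life questionnaire (EQ-5D-5L) at 3 months after the randomization will be summarized using appropriate descriptive statistics by treatment".

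SAP section 15.3 says the biomarkers "will be summarized using descriptive statistics by visit and treatment".

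SAP section 4.4 says: "For primary and secondary efficacy endpoints, p-value, lower and upper 95% Confidence Limits (CL) will be also presented". That sentence goes on to tie the p-values and limits to whatever analysis is performed. SAP section 18 lists four changes from the protocol, and the loss of these tests is not one of them.

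**The concern.** Three endpoints that the protocol puts under a testing commitment reach the final analysis with no specified contrast, and nothing in the SAP says so. This does not look like a general retreat to description after enrolment stopped at 68 patients (SAP section 4.3). The same SAP keeps arm-against-placebo comparisons for hospitalisation and intensive care admission (section 14.1.2, items 5 and 6), for both adverse event grade groups (section 15.1.2), and for PCR at days 14 and 28.

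NEWS matters most. It enters a comparison only through a cut at 2, combined with mechanical ventilation: at day 14 in section 14.1.1, at days 7 and 28 in section 14.1.2, and as a time to relief. Protocol section 4 defines a paucisymptomatic case by NEWS of 2 or below. Patients who fit that definition already satisfy the NEWS part of the relief event at entry, so the time-to-event analysis is a poor substitute for comparing scores. In a trial this small, discarding the rest of the scale is a real loss. A contrast chosen after unblinding would also carry less weight than one fixed beforehand.

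**Working it through.** **1. Commitment against specification.**

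| Endpoint | Protocol | SAP |
|---|---|---|
| NEWS category | test (9.5.2.2) | frequency and percent (14.1.2 item 3) |
| NEWS score | test (9.5.2.2) | descriptive (14.1.2 item 4) |
| EQ-5D-5L | test (9.5.2.2) | descriptive (14.1.2 item 8) |
| Biomarker change | test (9.5.2.2), but laboratory tests descriptive (9.5.4) | descriptive (15.3) |
| NEWS cut at 2, days 7 and 28 | test (9.5.2.2) | repeated measures logistic regression (14.1.2 item 2) |

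The first three rows are a plain mismatch. The fourth is ambiguous within the protocol itself.

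**2. The plan's own figure.** The documents give no power or sample size for NEWS score, EQ-5D-5L or biomarkers. Their error-control figure is the boundary of 2.69640 in Protocol section 9.3. Two doses by two endpoints gives 0.025 / 4 = 0.00625 one-sided per comparison. The two-look Pocock constant at that level, with looks at 50% and 100% of information, is 2.6964, which matches. All the planned alpha is therefore assigned to the four primary comparisons, and an exploratory secondary contrast takes none of it.

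**3. Information kept by a cut.** For a roughly normal outcome cut where a fraction q fails, the asymptotic efficiency relative to analysing the score is A(q) = φ(z)² / [q(1 − q)], with z = Φ⁻¹(q). Protocol section 9.1 plans success of 50% on placebo and 75% on treatment, so q runs from 0.50 to 0.25. The values 0.10 to 0.20 are an assumption, prompted by the entry definition of NEWS 2 or below.

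| q | Source | A(q) | 1 / A(q) |
|---|---|---|---|
| 0.50 | planned, placebo | 0.3989² / 0.25 = 0.64 | 1.6 |
| 0.25 | planned, treated | 0.3178² / 0.1875 = 0.54 | 1.9 |
| 0.20 | assumed | 0.2800² / 0.16 = 0.49 | 2.0 |
| 0.15 | assumed | 0.2332² / 0.1275 = 0.43 | 2.3 |
| 0.10 | assumed | 0.1755² / 0.09 = 0.34 | 2.9 |

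The last column is the factor by which the sample would have to grow for the cut endpoint to match the score.

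**4. Check on a discrete score.** NEWS is a small integer, so the normal formula is only a guide. A simulation (4,000 runs) used 23 patients per arm (68 / 3 = 22.7), two-sided 0.05, and a proportional odds ratio of 3, which is what 50% to 75% implies (odds 1 to 3). It compared a Wilcoxon test on the score with a z-test on NEWS of 2 or below. The spread of NEWS values was assumed, because no document gives it.

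| Placebo with NEWS ≤ 2 | Power, full score | Power, cut at 2 |
|---|---|---|
| 50% (planned) | 54% | 42% |
| 80% (assumed) | 51% | 23% |
| 90% (assumed) | 45% | 9% |

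The direction is the same throughout, and power on the full score never reaches 55%. Neither test is covariate-adjusted, so these figures compare the two scales and do not predict the SAP's models.

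**5. Size of a full remedy.** The biomarker list covers 13 haematology parameters, 4 hepatic (ALT, AST, total and direct bilirubin), 3 coagulation and 3 other markers, 23 in all. Over 4 visits and 2 doses that is 23 × 4 × 2 = 184 contrasts. NEWS score needs 3 × 2 = 6, and the EQ-5D-5L dimensions 5 × 2 = 10. Testing all 200 at 0.05 would give about 10 nominally significant results by chance. The 6 NEWS contrasts are a modest addition; the 184 are not.

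**The case against.** Much can be said for the SAP, and several stronger readings fail.

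- A reader might infer that NEWS is never compared between arms. It is compared, after the cut, at days 7, 14 and 28 and as a time to event.
- A reader might infer that SAP section 4.4 flatly contradicts section 14.1.2. Its qualifier ties p-values and limits to the analyses performed, so the two passages need reconciling but do not clearly conflict.
- A reader might infer that the biomarkers were wrongly stripped of tests. Protocol section 9.5.4 itself describes laboratory tests descriptively, so the protocol points both ways.
- A reader might infer that analysing the score is worth two to three times the sample. That needs a 10-20% failure rate, which the documents do not give. At their planned rates the factor is 1.6 to 1.9.
- The protocol does not name the contrast to be tested. Reading it as each dose against placebo is an inference, though the natural one in a placebo-controlled superiority trial.
- The default summaries in SAP section 4.4 include n, mean and SD, so a reader could compute a crude mean difference with its interval.

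With about 23 patients per arm, describing lower-priority endpoints is also defensible, and Protocol section 9.5.8 lets deviations be documented in the clinical study report. All of this narrows the point. It does not explain why the tests were dropped, nor supply a prespecified, baseline-adjusted NEWS estimate.

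**Conclusion.** The point holds in a limited form. For NEWS score, NEWS category and EQ-5D-5L, the SAP departs from the protocol's commitment to tests and does not declare it. As a result NEWS is compared only after being cut at 2. If the score is roughly normal, the cut keeps about 54-64% of the information at the planned failure rates, and 34-49% if failures are as rare as 10-20%. Entry at NEWS of 2 or below makes low failure plausible, but no document gives the distribution.

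The simulated advantage of the full score rests on an assumed spread of values and a large effect (odds ratio 3). For biomarkers the finding is only that the protocol is internally ambiguous. A reader might infer that the trial's main conclusions are compromised. They are not: the primary analyses and their error control are untouched.

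**What to change.** In SAP section 14.1.2, item 4, add an exploratory comparison of NEWS score at days 7, 14 and 28 for each dose against placebo, adjusted for baseline NEWS, which section 8.1 already uses as a covariate. Use a proportional-odds or rank-based method if the score is skewed. Report the estimate and 95% CI, labelled as unadjusted for multiplicity. State that patients withdrawn on meeting oxygen criteria (Protocol section 6.2.4) may lack later scores, so the highest values may be missing.

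For EQ-5D-5L, which has no baseline measurement in the schedule, and for the biomarkers, either name a short list of exploratory contrasts or record the descriptive-only choice in section 18 and align section 4.4 with it. If NEWS category stays descriptive, record that in section 18 too. Settle this before unblinding.

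The cost is SAP wording and a few extra tables, with no new data. The drawback is low power, so the results should be read as estimates with wide intervals.
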